3.6 Concomitant and post-treatment therapy

Concomitant therapies

Concomitant therapy is defined as all interventions (therapeutic treatments and procedures) besides the study treatment that were administered to a patient, coinciding with the study assessment period (even if started before the study assessment period).

Concomitant medications will be coded using the World Health Organization (WHO) Drug Reference Listing (DRL) dictionary that employs the WHO Anatomical Therapeutic Chemical (ATC) classification system.

Concomitant medications will be summarized by lowest ATC class, preferred term and treatment arm. The summary will include medications starting on or after the start of study treatment but no later than 30 days after last dose of study treatment or before the start of open-label ribociclib plus NSAID plus goserelin treatment

The safety set will be used for all concomitant medication tables and listings.

Concomitant medications will be listed also for the cross-over period using the cross-over analysis set. Any concomitant therapies starting more than 30 days after the last date of cross-over open-label study treatment will be flagged in the listing.

3.7 Safety evaluation

The assessment of safety will be based mainly on the frequency of adverse events and on the number of laboratory/ECG values that fall outside of pre-determined ranges. Other safety data (e.g., vital signs and special tests) will be considered as appropriate.

All safety outputs will use the safety set. The safety summary tables will include ‘double-blinded on-treatment’ events/assessments, i.e., those collected on or after the first date of study treatment and collected no later than 30 days after the date of last study treatment administration or the date of the day prior to the start of cross-over open-label ribociclib plus NSAID plus goserelin treatment. The AEs started before the first dose but worsening during the treatment period are also considered as ‘on-treatment’ events.

Key safety analyses that include data from the cross-over on-treatment period will also be performed on the cross-over analysis set. See Section 2.1.8 for more details on the definition of ‘on-treatment’ event during the cross-over on-treatment period.

3.7.1 Adverse events (AEs)

3.7.1.1 Coding of AEs

Adverse events are coded using the Medical Dictionary for Regulatory Activities (MedDRA) terminology.

3.7.1.2 Grading of AEs

AEs will be assessed according to the Common Terminology Criteria for Adverse Events (CTCAE) version 4.03.

The CTCAE represents a comprehensive grading system for reporting the acute and late effects of cancer treatments. CTCAE v4.03 grading is by definition a 5-point scale generally corresponding to mild, moderate, severe, life threatening, and death.

If CTCAE grading does not exist for an adverse event, grades 1 – 4 corresponding to the severity of mild, moderate, severe, and life-threatening will be used. CTCAE grade 5 (death) will not be used in this project; if an AE results in death it will be documented in the outcome (“fatal”). Information on deaths will also be collected on the ‘Death’ CRF.

3.7.1.3 General rules for AE Reporting

AE summaries will include all AEs starting on or after study Day 1 (i.e., on or after the day of the first intake of study treatment) and starting no later than 30 days after the last administration of study treatment or the date of the day prior to the start of cross-over open-label ribociclib plus NSAID plus goserelin treatment (see [Section 2.1.5](#)). All AEs will be listed. AEs starting prior to study Day 1 and AEs starting later than 30 days after the last treatment date or the date of the day prior to the start of cross-over open-label ribociclib plus NSAID plus goserelin treatment will be flagged in the listings. AEs starting during the cross-over on-treatment period will be listed separately.

AEs will be summarized by presenting the number and percentage of patients having at least one AE, having at least one AE in each primary system organ class, and for each preferred term using MedDRA coding. A subject with multiple occurrences of an AE will be counted only once in the AE category.

Separate AE summaries will be presented by primary system organ class, preferred term, and maximum grade. A patient with multiple grades for an AE will be summarized under the maximum grade recorded for the event. AE with missing CTCAE grade will be included in the ‘All grades’ column of the summary tables.

In AE summaries the primary system organ class will be presented alphabetically and the preferred terms will be sorted within primary SOC in descending frequency. The sort order for the preferred term will be based on their frequency in the ribociclib arm.

The frequency of grade 3 and 4 AEs will be summarized separately.

Any information collected (e.g. grades, relationship to study treatment, action taken etc.) will be summarized and listed as appropriate.

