## Amendment 6 (18-Jul-2019)

Study CLEE011E2301 was initiated in November 2014 and completed enrollment on 01-Aug-2016 with a total number of 672 randomized patients. The study met its primary endpoint of progression-free survival (PFS) at the time of the primary analysis in October 2017. The study met its key secondary endpoint of overall survival (OS) at the time of the planned second OS interim analysis in February 2019. Given these results, study participants will be unblinded in preparation for study closure. In addition, patients who are still receiving study treatment in the placebo arm, will be allowed to cross over to the ribociclib arm, based on the Investigator's judgement and an individualized benefit risk decision.

As of 03-July-2019, there are still 135 patients ongoing on study treatment, including 89 patients on ribociclib and 46 patients on placebo.

The purpose of this amendment is to:

- i. Unblind patients and investigators in order to allow for knowledge of patient's current treatment allocation
- ii. Allow for patients receiving placebo the opportunity to cross over to treatment with LEE011 per Investigator discretion
- iii. Provide guidance for patients receiving placebo + tamoxifen, who as per Investigator discretion will cross over to LEE011, to switch to an NSAID, if they are to cross over to treatment with LEE011. These patients will complete a wash out period of 5 half-lives.
- iv. Clarify end of study (EOS) and include information on post-study drug access
- v. Specify that central safety assessments can cease and all laboratory and ECG assessments should be performed locally and clarify the frequency of assessments
- vi. Specify that patient reported outcome (PRO) measures should no longer be collected  
[REDACTED]
- viii. Update the laboratory assessments to remove phosphorous and, per the IB, add serum pregnancy testing at EOT

Following this protocol amendment and the unblinding of study participants, the word "placebo" refers to the original treatment allocation in the study. Physical placebo capsules no longer need to be administered but the wording has been kept in places in the protocol to avoid confusion.

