### **6.1.5 Treatment duration**

Patients may continue study treatment until disease progression (radiologically documented according to RECIST 1.1), or until discontinuation of study treatment due to any other reason (see [Section 7.1.5](#)).

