2.1.8 On-treatment assessment/event

Safety summaries and selected summaries of deaths will summarize only on-treatment assessments/events.

Double-blind on-treatment period:

An on-treatment assessment/event is defined as any assessment/event in the following time interval:

[date of first administration of study treatment, the earliest between the date of last administration of study treatment + 30 days and the date of first administration of cross-over open-label ribociclib plus NSAID plus goserelin treatment – 1 day], i.e., including the lower and upper limits.

The double-blind on-treatment period is the **default** on-treatment period used in the analyses unless specified otherwise.

Cross-over on-treatment period:

An on-treatment assessment/event is defined as any assessment/event in the following time interval: [date of first administration of the cross-over open-label ribociclib plus NSAID plus goserelin treatment, date of last administration of the cross-over open-label ribociclib plus NSAID plus goserelin treatment + 30 days], i.e., including the lower and upper limits.

(Note: However, the calculation of study treatment duration will use different rules as specified in [Section 3.5.1](#)).

An AE started in the screening phase and ongoing in the on-treatment phase will not be considered as an on-treatment AE unless it has worsened.

If the last date of study treatment is missing, any assessment/event occurring after the start of study treatment will be considered as on-treatment.

Data listings will include all assessments/events, flagging those which are not on-treatment.

Note: The date of first administration of study treatment and the date of last administration of study treatment are defined in [Sections 2.1.4](#) and [2.1.5](#), respectively.

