3.7.1.4 AE summaries

The following adverse event summaries will be produced by treatment group:

- Summary of deaths and adverse events
- Adverse events, irrespective of causality, by primary system organ class, preferred term and maximum grade

- Adverse events with suspected relationship to study treatment by primary system organ class, preferred term and maximum grade
- Most common grade 3-4 adverse events, irrespective of causality, by preferred term and maximum grade (greater than x% in either arm)
- Adverse events, irrespective of causality, by primary system organ class and maximum grade
- Adverse events, irrespective of causality, by preferred term and maximum grade
- Adverse events with suspected relationship to study treatment by preferred term and maximum grade
- On treatment deaths by preferred term
- Deaths, by primary system organ class and preferred term
- Serious adverse events, irrespective of causality, by primary system organ class and preferred term and maximum grade
- Serious adverse events with suspected relationship to study treatment, by primary system organ class, preferred term and maximum grade
- Adverse events leading to study drug discontinuation, irrespective of causality, by primary system organ class, preferred term and maximum grade
- Adverse events leading to study drug reductions, irrespective of causality, by primary system organ class, preferred term and maximum grade
- Adverse events leading to study drug interruptions, irrespective of causality, by primary system organ class, preferred term and maximum grade
- Adverse events requiring additional therapy, irrespective of causality, by primary system organ class, preferred term and maximum grade
- On-treatment deaths and SAEs with fatal outcome, by SOC and PT

AEs of interest will also be summarized. See [Section 3.7.1.5](#) for the grouping details.

Subgroup analyses by endocrine combination partner subgroups (tamoxifen and goserelin; NSAID and goserelin) will be performed for the analysis of adverse events, irrespective of causality, by primary system organ class, preferred term and maximum grade.

Separate summaries will be provided for adverse events, deaths and serious adverse events occurring during the cross-over on-treatment period for the cross-over analysis set.

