3.7.1.5 Grouping of adverse events of special interest

An adverse event of special interest is a grouping of adverse events that are of scientific and medical concern specific to ribociclib. These groupings are defined using MedDRA terms, SMQs (standardized MedDRA queries), HLGs (high level group terms), HLTs (high level terms) and PTs (preferred terms). Customized SMQs (Novartis MedDRA queries, NMQ) may also be used. A NMQ is a customized group of search terms which defines a medical concept for which there is no official SMQ available or the available SMQ does not completely fit the

need. It may include a combination of single terms and/or an existing SMQ, narrow or broad. For each specified AESI, the number and percentage of patients with at least one event of the AESI occurring during the double-blinded on-treatment period will be summarized.

Summaries of these AESIs will be provided by treatment arm, (specifying grade, SAE, relationship, leading to treatment discontinuation, leading to dose adjustment/interruption, etc.).

A Case Retrieval Sheet (CRS) with the exact composition of the AE groupings is to be used to map reported AEs to the AESI groupings. This file may be updated (i.e., it is a living document) based on review of accumulating trial data, and therefore the groupings are also subject to potential change. The most up-to-date version of the CRS will be used at the time of the analysis.

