- Listing of all laboratory data with values flagged to show the corresponding CTC grades and the classifications relative to the laboratory reference ranges.

Time to first occurrence of grade 2 or worse laboratory toxicity and time to first occurrence of grade 3 or worse laboratory toxicity will be performed for (i) neutropenia and (ii) ALT/AST. Median time to first occurrence and 95% CI will be provided based on the Kaplan-Meier method. In addition, Kaplan-Meier plots will be generated.

Time to first occurrence of grade X or worse laboratory toxicity is defined as the time from the start of treatment to the start date of the first incidence of grade X or worse laboratory toxicity, i.e. time in days is calculated as (start date of first occurrence) – (date of first dose of study treatment) + 1. A patient will be censored if:

- The patient did not report any post-baseline grade X or worse event on or before the analysis cut-off date.
- The patient discontinued treatment without reporting any grade X or worse event up to 30 days after study treatment discontinuation.
- The patient died without reporting any grade X or worse event.
- The patient received a new anticancer therapy before reporting any grade X or worse event.

The censoring date will be the earliest of the following dates: end of treatment + 30 days, analysis cut-off, new anti-cancer therapy start date, death date and last non-missing assessment for the lab parameter. Note that patients who have grade X or worse toxicity at baseline or missing baseline evaluation will be excluded from this analysis.

In addition, the median time to first occurrence for the subset of patients who experienced the event of interest will be calculated. Simple descriptive statistics, median, min and max as well as 25th percentile and 75th percentile, will be presented.

Duration of grade X or worse laboratory toxicity may also be summarized. Duration of grade X or worse event is calculated as:

(Date when the grade of the event decreases to below X) – (date of onset of grade X or worse event) + 1

For patients experiencing any grade X or worse event, the duration of the first such event will be summarized using the Kaplan-Meier method. Median duration and 95% CI will be presented. In addition, Kaplan-Meier plots will be generated.

A patient will be censored for the duration of grade X or worse event, if:

- The patient dies without reporting a decrease to below grade X

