3.9.4 ECG

All analyses of ECG data will be based on the average of all available replicate ECGs assessed at each time point for each patient. For unscheduled assessments, 15-minute windows will be applied to group assessments for averaging.

ECG data will be summarized by presenting summary statistics of the raw data and change from baseline by treatment arm and time point. The following parameters will be assessed: QT, QTcF, QTcB, PR, and QRS intervals in msec, heart rate (bpm), and the overall interpretation if clinically significant abnormalities are present.

The number and percentage of patients with notable abnormalities will be summarized. Summary statistics and shift tables will be presented. Individual listings will be provided by subject.

Table 3-8 Clinically notable ECG values

ECG parameter (unit)	Clinically notable criteria
QT, QTcF, QTcB (ms)	New > 450
	New > 480
	New > 500
	Increase from Baseline > 30
	Increase from Baseline > 60
PR duration (ms)	Increase > 25% from baseline and to PR duration > 200 New > 200
QRS duration (ms)	Increase > 25% from baseline and to QRS duration > 110 New > 110
Heart Rate (bpm)	< 50 and decrease from Baseline of > 25%
	> 100 and increase from Baseline of > 25%

A newly occurring ECG abnormality is defined as an abnormal post-baseline ECG finding that is not present at baseline. Baseline is defined as the average of the last replicate ECG measurements taken

on or before treatment start date. The percentage of patients having notable ECG interval values is based on the number of patients at risk for the change with a value at baseline and post-baseline.

Time to grade 2 or worse QT prolongation will be analyzed using the Kaplan-Meier method and the median time to grade 2 or worse QT prolongation will be presented along with a 95% confidence interval if there are sufficient numbers of events for each treatment group.

In addition, the median time to event for the subset of patients who experienced grade 2 or worse QT prolongation will be calculated. Simple descriptive statistics, median, min and max as well as 25th percentile and 75th percentile, will be presented.

Note that patients who have grade 2 or worse toxicity at baseline or missing baseline evaluation will be excluded from these analyses.

ECG by dose group will also be explored as described in [Section 3.10.4.3](#).

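### The final safety report compares crude AE percentages over a window that is probably longer on ribociclib; for AEs that accrue throughout treatment this alone produces an apparent excess, so exposure-adjusted rates and time-to-first-event analyses should be added

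*SAP*

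**What the plan says.** The SAP file holds two plans, one for the primary PFS analysis and one for the final CSR. This point concerns the second.

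- **Metric.** Section 3.7.1.3: "AEs will be summarized by presenting the number and percentage of patients having at least one AE", each patient counted once per category. Section 3.7.1.4 introduces its table list with "The following adverse event summaries will be produced by treatment group"; SAEs are in that list. For AESIs, 3.7.1.5 says that "the number and percentage of patients with at least one event of the AESI occurring during the double-blinded on-treatment period will be summarized".
- **Window.** Section 2.1.8 opens the default on-treatment period at first dose. It closes at "the earliest between the date of last administration of study treatment + 30 days and the date of first administration of cross-over open-label ribociclib" combination treatment less one day. Last administration means the last dose of any component (2.1.5).
- **Duration.** Protocol 6.1.5 lets treatment continue until documented progression or another reason to stop. Protocol Amendment 6 records that the PFS endpoint was met and that 135 patients were still on treatment in July 2019, "including 89 patients on ribociclib and 46 patients on placebo".
- **Exposure.** Section 3.5.1 summarises duration of exposure by arm and in time bands. Nothing links it to the AE tables. The disclosure tables in 3.7.1.6 also count occurrences, but without person-time.
- **Primary-analysis SAP.** It planned more. Section 3.9.2 includes "Time to first occurrence of grade 2 or worse laboratory toxicity" (and grade 3 or worse) for neutropenia and ALT/AST. Section 3.9.4 says "Time to grade 2 or worse QT prolongation will be analyzed using the Kaplan-Meier method". The corresponding final-CSR sections (3.7.2, 3.7.4) contain neither.

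**The concern.** A percentage of patients with at least one event mixes the event rate with the time each patient was observed. If one arm is observed longer because its patients progress later, an AE that arises at the same rate in both arms reaches a higher percentage in the arm with better efficacy. Someone reading the final tables cannot separate that from real toxicity, and cannot tell which AEs arise early and which build up over time.

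Safety and tolerability is a stated secondary objective, and follow-up is longest in the final report. The tables are descriptive, so type I error is not at stake. What is at stake is how background and late events are attributed.

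**Working it through.** **Step 1. The plan's own figures.** Protocol 10.8 gives HR 0.67, one-sided 2.5%, 95% power, 329 events, and medians of 9 and 13.4 months. Schoenfeld: 4(1.960 + 1.645)² / (ln 0.67)² = 51.98 / 0.1604 = 324.1, so 325 events. Freedman gives 333, and power at 329 events is 95.3%. The treated median is 9 / 0.67 = 13.4 months. The stated figures reproduce.

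**Step 2. How unequal is exposure?** No observed treatment durations by arm are given, so two proxies are used, both assuming exponential time on treatment.

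- *Planned medians.* Mean = median / ln 2: 9 / 0.693 = 12.98 and 13.4 / 0.693 = 19.33 months, ratio 1.49. Truncated at 45 months: 12.58 and 17.45, ratio 1.39.
- *July 2019 counts.* With 672 randomised 1:1, assume 336 per arm: 46/336 = 13.7% and 89/336 = 26.5% on treatment. Assume about 45.5 months since randomisation. The stopping hazards are −ln(0.137)/45.5 = 0.0437 and −ln(0.265)/45.5 = 0.0292 per month. Truncated means (1 − proportion on treatment)/hazard are 19.75 and 25.18 months, ratio 1.27. Arm sizes of 330 to 342 give 1.26 to 1.29 truncated and 1.46 to 1.53 untruncated; 40 to 52 months of follow-up leaves the ratios unchanged.

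About 1.3 to 1.5 is therefore supportable. Amendment 7's counts for January 2020 point the same way: 79/336 = 23.5% against 35/336 = 10.4%, with 8 of the 35 crossed over.

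**Step 3. Equal true rates, constant over treatment.** Let λ be the AE hazard, μ the stopping hazard and w = 30/30.4375 = 0.986 months the tail after last dose. Then

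P(at least one AE) = 1 − exp(−λw) × μ/(λ + μ).

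At λ = 0.01 per month (12 per 100 patient-years) under the planned medians:

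- placebo: μ = 0.0770; 1 − 0.9902 × 0.0770/0.0870 = 12.4%
- ribociclib: μ = 0.0517; 1 − 0.9902 × 0.0517/0.0617 = 17.0%

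The count-based columns replace μ/(λ + μ) by its form truncated at τ = 45.5 months, μ/(λ + μ) × (1 − e^(−(λ+μ)τ)) + e^(−(λ+μ)τ).

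| True rate, both arms (per 100 PY) | Planned medians: placebo / ribociclib | Ratio | On-treatment counts: placebo / ribociclib | Ratio |
|---|---|---|---|---|
| 1.2 | 1.4% / 2.0% | 1.45 | 2.0% / 2.6% | 1.26 |
| 12 | 12.4% / 17.0% | 1.38 | 17.8% / 22.0% | 1.23 |
| 24 | 22.2% / 29.3% | 1.32 | 31.0% / 37.6% | 1.21 |
| 60 | 42.3% / 51.6% | 1.22 | 54.9% / 63.3% | 1.15 |
| 240 | 77.2% / 83.1% | 1.08 | 85.3% / 89.5% | 1.05 |

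The true rate ratio is 1.00 in every row. The largest gap in the table is 9.3 points.

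**Step 4. Early-onset AEs.** Take an equal hazard of 0.2 per month for two months and none afterwards, with the planned medians. Crude percentages are 30.7% and 31.4% without the tail, and 32.4% and 32.6% with it (ratio 1.01). The crude metric is almost unbiased here.

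The patient-year rate is not. Mean time at risk to first event is about 9.67 and 13.93 months, so the rates are 0.324/9.67 × 1200 = 40 and 0.326/13.93 × 1200 = 28 per 100 patient-years, ratio 0.70. If ribociclib truly had 1.5 times the early hazard, the crude ratio would be 1.38 and the rate ratio 1.15. Rates alone would then understate a real harm.

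**The case against.** The strongest counter-argument is about scope. Protocol 1.2.1.3 says neutropenia usually starts by Day 15 and QT changes appear in the first cycle, by Day 8. Protocol 1.4.1.1 lists neutropenia, QT prolongation and hepatobiliary toxicity as the important identified risks. For the first two, nearly all patients in both arms pass through the risk period, so crude percentages are adequate, and step 4 shows that patient-year rates would mislead. This stands. It limits the point to AEs that accrue over time and rules out basing every between-arm statement on rates.

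Second, PFS medians are not treatment durations. Patients stop for other reasons, and the window follows the last dose of any component, including endocrine therapy continued after ribociclib or placebo stops (Protocol 6.1.4). This also stands, and is why only a range is given.

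Third, the protocol's endpoint is the frequency and severity of AEs, and Protocol 10.5.3.2 specifies incidence. The SAP delivers that, reports exposure separately, and tabulates suspected-related events. All true. But the separate exposure summary shows an imbalance without correcting any AE for it.

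Fourth, the Kaplan-Meier safety analyses were already planned for the primary CSR, which would have captured most early first events, so omitting them from a close-out plan is defensible. Fair. Still, once rates are added, the curves are needed to show where the rates can be trusted.

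**Conclusion.** The point holds for AEs with a roughly constant hazard throughout treatment. For these, the planned tables would show an excess on ribociclib even if the true rates were equal. The crude ratio is about 1.2 to 1.4 at 12 per 100 patient-years and shrinks towards 1 for near-universal AEs. For AEs confined to the first months the effect is negligible.

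The size rests on exponential time on treatment, assumed arms of 336, and planned medians or on-treatment counts in place of observed durations.

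A reader might infer three stronger things that the documents do not support:

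- *That ribociclib's known toxicities are exposure artefacts.* The protocol's own onset data for neutropenia and QT change argue against this.
- *That ribociclib patients were treated very much longer.* No observed durations are given, and 1.3 to 1.5 is as far as the figures go.
- *That the SAP departs from the protocol.* It does not; this is an inexpensive gain in interpretability.

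**What to change.** Keep all planned percentages. In final-CSR SAP 3.7.1.4 and 3.7.1.5 add, by arm, patients with a first event per 100 patient-years at risk, with 95% CI, for all AEs, grade 3-4 AEs, SAEs and each AESI. Time at risk runs from first dose to the first event or the end of the window in 2.1.8.

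Add Kaplan-Meier or cumulative-incidence analyses of time to first event for AESIs, and carry over the neutropenia, ALT/AST and QT analyses from the primary-analysis SAP (3.9.2, 3.9.4).

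State how the outputs are to be read:

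- late-accruing AEs with the rates;
- early-onset AEs with the time-to-event curves or the percentages;
- patient-year rates assume a roughly constant hazard and understate the ribociclib-to-placebo ratio for early-onset events.

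The cost is a few more tables and figures. Dosing and event dates already feed the planned derivations, so no new data are needed.
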